4.2.2 Temperature stability and regulation	11
4.2.3 Usability	11
4.2.4 Adverse events	11
4.2.5 Staff feedback	11
5. STUDY DESIGN	11
6. STUDY PROCEDURES	12
6.1 Recruitment	12
6.2 Procedure	13

6.3 Inclusion / Exclusion Criteria	14
6.3.1 Inclusion criteria	14
6.3.2 Exclusion criteria	14
6.4 Withdrawal of Patients from the study	14
7. ADVERSE EVENTS	15
7.1 Adverse event (AE)	15
7.2 Anticipated Adverse Event	15
7.3 Serious Adverse Events	15
7.4 Reporting of Adverse Events	15
8. STATISTICS AND DATA ANALYSIS	19
9. ETHICS	20
9.1 Declaration of Helsinki	20
9.2 Independent Ethics Committee Approval	20
9.3 Informed Consent	20
10. SUBJECT CONFIDENTIALITY	20
11. DATA MANAGEMENT	20
11.1 Data Quality Assurance	21
11.2 Data Storage at the end of the study	21
12. FINANCING AND INSURANCE/INDEMNITY	22
13. CLINICAL SUPPLIES	22
14. REPORTING AND DISSEMINATION OF STUDY OUTCOMES	22
15. REFERENCES	22
16. INVESTIGATOR APPROVAL STATEMENT	24

ii. KEY STUDY CONTACTS

Chief Investigator (CI) and Medical Expert	[name], Neonatology Consultant, Ashford and St Peter's Hospitals NHS Foundation Trust, St Peter's Hospital, [name] [contact] [name]
Study Co-ordinator (Project manager)	[name], Director of Clinical Affairs, mOm Incubators Limited [contact] [name]
Sponsor	mOm Incubators Limited, [name] www.mominubators.com
Funder	Sponsor funded: mOm Incubators Limited
Key Protocol Contributors	[name] and mOm Incubators Limited

iii. CLINICAL INVESTIGATION PLAN AMENDMENT HISTORY

Amendment No.	CIP Version No.	Date issued	Author(s) of changes	Details of Changes made
N/a	1.0	10 April 2018	[name], [name] (statistician) and [name]	Original Clinical Investigation Plan
1	2.0	23 July 2021	[name]	Title Updated Dates and staff role/details updated. Adverse event causality updated to MDR/MDCG guidance requirements.
2	3.0	09 March 2022	[name]	Updated to clarify when recordings are required for each

				clinical data parameter and updated target recruitment period.
--	--	--	--	--

iv. STUDY SUMMARY

Study Title	Comparison of the mOm incubator with a standard incubator for the maintenance of thermal stability in infants ($\leq 6\text{kg}$)
Internal ref.	mOm/2018/01
Study Design	Prospective, multi-centred, randomised, controlled, cross-over study
Study Subjects	Babies at least 30 weeks Gestational age (GA) that are clinically stable but require at least 48 hours thermoregulated incubator care
Planned Size of Sample (if applicable)	36 completed subjects
Planned participation duration	48 hours per subject
Planned Study Period	Until recruitment is complete (target of nine months maximum recruitment period)
Research Question/Aim(s)	The study will compare the level of thermal care delivered to a clinically stable baby in the mOm incubator and a standard (non-humidified) incubator. Staff feedback on the experience of using the mOm incubator will also be collected.

v. ROLE OF SPONSOR AND INVESTIGATOR

[name] is the CI for this study and will be involved in all aspects of the study oversight. Both the CI and Principal Investigator (PI) at any other site(s) involved in the study are responsible for conduct of the study at their site and delegation of authority to appropriately qualified, and GCP trained, staff. This includes Sub/Co-investigators (SIs) (other consultants), research nurses (RNs) and any other members of the clinical research team. The CI and PI must complete a 'Delegation of Authority Log' detailing who may perform which study tasks including: gaining written informed consent from subjects' parents/legal guardians, recruitment, conduct of study data collection, completion / maintenance of study records and site files, and the final sign-off of each subject Case Report Form (CRF).

The investigators and Sponsor project manager are responsible for providing appropriate training for staff involved in the study and writing up the results of the study and management of their publication and appropriate dissemination.

[figure not shown]
The Sponsor is funding the study, providing the mOm incubators, study management and data collection documentation and will be responsible for conducting source data verification (SDV) and checking site adherence to the CIP.

[name] from the Faculty of Medicine at Southampton University, has provided statistical advice for this study.

vi. LIST OF ABBREVIATIONS

ADE	Adverse Device Event
AE	Adverse Event
CI	Chief Investigator
CIP	Clinical Investigation Plan
CRF	Case Report Form
GA	Gestational Age
GCP	Good Clinical Practice
GDPR	General Data Protection Regulations
GMP	Good Manufacturing Practice
HRA	Health Research Authority
IB	Investigator Brochure
ICF	Informed Consent Form
ISF	Investigator Site File
ISRCTN	International Standard Randomised Controlled Trials Number
MHRA	Medicines and Healthcare products Regulatory Agency
NHS R&D	National Health Service Research & Development
PI	Principal Investigator
PIS	Subject Information Sheet
REC	Research Ethics Committee
RN	Research Nurse
SADE	Serious Adverse Device Event
SAE	Serious Adverse Event
SDV	Source Data Verification
SI	Sub-Investigator (consultants working on the study with delegated responsibility from the PI/CI)
SOP	Standard Operating Procedure
TMF	Trial Master File

vii. STUDY FLOW CHART

1. BACKGROUND

Prematurely born infants are nursed in incubators to provide a stable and warm environment, until they can maintain a stable temperature in an open / warmed cot. It has been known for decades that hypothermia in the premature infant can cause cold stress resulting in poor weight gain and metabolic stress^{1,2}. The baby maintains its normal temperature via hypothalamic control mechanisms, creating warmth (thermogenesis) through shivering and non-shivering mechanisms³. In the preterm or growth restricted baby, these mechanisms are less well developed, placing them at additional risk. In the developing world, hypothermia is associated with significant mortality especially in these higher risk patients⁴.

1.1 Standard Practice

In the developed world, premature and growth restricted babies generally have access to sophisticated conventional incubators in hospital, which provide uniform and controlled temperature to minimise thermal stress. Generally, all babies born less than 1500g would normally be cared for in an incubator until they are able to regulate their temperature outside of a controlled environment; this cut-off varies between hospitals (e.g. 1400g at St Peter's hospital, London, but 1500g at St Mary's hospital, Manchester).

1.2 mOm Incubator

The mOm Incubator (trade name mOm Essential Incubator) is a infant incubator designed to provide a level of thermoregulation that meets the standards set for conventional incubators whilst being low cost and space-saving. [name] (CEO of mOm Incubators Limited) invented the mOm incubator after watching a documentary on Syria where he learned that, because of the stress of war, infant mortality rates have soared causing the country to lose nearly an entire generation to preventable infant deaths. The incubator design was part of his Design Engineering course at Loughborough University; he went on to win the Sir James Dyson Global Prize for Innovation in 2014.

2. RATIONALE

The mOm incubator fulfils the need to provide incubator care for babies requiring thermoregulation where standard incubators may not be available, such as in low to medium income countries.

This study aims to compare the ability of the mOm incubator to provide an adequate thermoregulated environment when used in a clinical setting using a prospective, multi-centre, randomised, cross-over study design to provide a direct comparison with standard incubators. It is hoped that the results of this study and the introduction of the mOm incubator could help to improve the survival rates of preterm babies born in places where access to expensive standard incubators is limited or not available.

The hypothesis is that the mOm incubator will perform as well as a standard incubator for routinely maintaining temperature stability in the baby.

2.1 Assessment of benefits / risks and management of risk

2.2.1 Benefits

The only direct benefit for subjects in this study is that the participating babies will be more closely observed than in standard care for babies fitting the inclusion criteria.

2.1.2 Risks and Management of Risk

The mOm incubator has been carefully designed to maintain a stable temperature environment for the baby.

The mOm infant incubator been manufactured under current Good Manufacturing Practice (GMP), designed and tested to provide a level of thermoregulation that meets the harmonised standards set for conventional baby incubators (BS EN 60601-2-19)^{5,6}. More information and testing results for the mOm incubator will be provided to the site clinical research team in the form of an Investigator Brochure (IB). The clinical research team will have full control and responsibility for the baby's care and can withdraw a subject from the study at any time for any reason. The risks should therefore be no more than for standard routine incubator care.

If for any reason the subject, or incubator, has any unforeseen serious adverse event whilst the baby is in the mOm incubator the subject will immediately be removed from the study and placed into standard care. Monitoring of the serious adverse event will be followed up and if the adverse event is a serious device adverse event, the study will be halted with immediate effect and only be continued when the Sponsor and Chief Investigator are confident that the issue is resolved and will not be repeated.

If there are any concerns about temperature stability (or any other matter) in any baby being nursed in the mOm incubator during the study, then standard protocols for clinical evaluation by a doctor will be followed. At the discretion of the attending clinician, the baby can be moved into a conventional (standard) incubator at any time without restriction. A spare standard incubator will always be available for this purpose.

If there are unexpected clinical incidents such as Serious Adverse Device Events (SADE) these will be reported to the Sponsor, the Research Ethics Committee (REC), Medicines and Healthcare products Regulatory Agency (MHRA), NHS Trust Research and Development as well as through the normal NHS Trust Risk reporting mechanisms (Datix).

Photographs and/or video recordings of the use of the mOm incubator may be taken during the study but will be taken in such a way so that the baby cannot be identified. The study will adhere to the principles outlined in the Declaration of Helsinki⁷, relevant Sponsor's SOPs and study- specific manuals included in the Investigator Site File (ISF) and Trial Master File (TMF), and, will follow the principles of GCP⁸.

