5. STUDY DESIGN

The study has a prospective, multi-centre, randomised controlled, cross-over design. There will be two arms to the research. The first arm will consist of mOm incubator

care for 24 hours, followed by a further 24 hours where the subject is transferred for care to a standard incubator. The second arm will consist of 24 hours care in a standard incubator followed by 24 hours care in a mOm incubator. The care of the baby (subject) is mostly unchanged from standard incubator care, but observations may be recorded more frequently (*i.e.* hourly) for incubator displayed temperatures and some other physiological measures of clinical stability than would normally be collected in routine care for this type of clinically stable baby of at least 30 weeks GA (normally every three hours) (See Table 1). No additional blood tests or any other invasive testing or monitoring are required. The clinical research team will have full control and responsibility for the baby's care, with the ability to withdraw the baby from the study at any time for any reason if they feel the baby is clinically unstable or is adversely affected by their environment. The order of incubator type in which the baby is cared for (*i.e.* which arm of the study) before being crossed over to the alternative incubator type will be assigned at random at the point of written consent being gained and the subject therefore having been officially recruited.

Babies that are considered clinically stable from a cardio-respiratory point of view but require at least 48 hours incubator care but not requiring additional humidification will be recruited to the study from the Neonatal Unit. In practice, this will mostly be babies weighing less than approximately 1400g at 30 weeks, although some term babies may also be eligible for the study if they are being nursed in an incubator for clinical reasons.

The aim is to collect 36 completed data sets for analysis; to achieve this approximately 40 babies will be recruited; recruitment will be stopped once 36 completed data sets are available. The target is to complete recruitment within a nine-month period.

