6.4 Withdrawal of Patients from the study

All subjects (via their parent/legal guardian) are free to withdraw from the study at any time for any reason without their standard of care being affected. If a patient is withdrawn before the completion of this study, the reason(s) for withdrawal will be documented where possible.

Withdrawal of a subject by a member of the clinical research team will occur for any of the following reasons:

- An unanticipated serious adverse event (e.g. SAE or SADE) which requires immediate change to alternative treatment.
- A protocol violation (*i.e.* violation of the inclusion/exclusion criteria during screening period or serious deviation from the clinical investigation plan, or guidelines during the study which may affect the integrity of the study or the patient's well-being).

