7. ADVERSE EVENTS

7.1 Adverse event (AE)

Any undesirable clinical occurrence in a subject, whether considered to be procedure related or not, that includes a clinical sign or symptom. Typical AEs which should be recorded include but are not limited to: skin injury or infection, pressure sores, hyperthermia, hypothermia, apnea and bradycardia. AEs also include Adverse Device Events (ADEs). ADEs are any undesirable device related event, whether clinically relevant to the subject or not. Typical device ADEs which should be recorded include but are not limited to: rainout, practical access issues, degradation of part of the incubator, inadvertent displacement of lines thought to be due to the design of the incubator.

AEs will be recorded from the time the subject has been enrolled and placed in the first incubator type until the end of their participation in the study (*i.e.* after 48 hours incubation is complete), unless a device related adverse event is on-going in which case it will be monitored until resolved. All AEs should be recorded in the patient notes, the CRF and on the Adverse Event log in the ISF.

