8. STATISTICS AND DATA ANALYSIS

The primary endpoint is babies' truncal skin surface temperature variation; also termed core or central temperature. This is expected to fluctuate but remain within normal temperature limits (36.5 to 37.5 degrees Celsius). Variations from this endpoint will be analysed and compared statistically between the two arms of the study.

Thirty-six completed datasets are required for the analysis to be valid. A complete subject dataset will be deemed acceptable if 19 of the 24, once-hourly temperature observations have been recorded for each incubator type (*i.e.* 79% compliance). This degree of compliance was considered acceptable for analysis because it is still greater than the routine standard for this type of incubator care for clinically stable infants of 30 weeks GA or greater, which is often every three hours. Although data analysis will be largely descriptive, the performance of the mOm incubator will be statistically quantified by assessment of the fluctuations of babies' temperatures during each 24-hour period. It is expected that these babies' temperatures will fluctuate by around one degree Celsius, and this is normal. Thus, analysis will explore whether fluctuations for each baby keep within this bound. A 95% confidence interval will be calculated around the mean of these fluctuations within each baby for each of the two incubators. Data from 36 babies would allow such a confidence interval to be calculated to within plus or minus 0.33 of a degree if the actual mean fluctuations are around one degree (*i.e.* as normally expected) and assuming a two-sided confidence interval.

Each patient will serve as their own control. The order of incubator type used for each of the two consecutive 24-hour periods of incubator care, and therefore which study arm the subject is recruited to, will be assigned randomly. A Microsoft Excel random number generation system will be used to generate random numbers with which the arm of the study which the subject is to enter will be assigned. Each assignment will be placed in an envelope attached to each CRF already numbered with a continuous series subject number.

Baseline demographic factors of the study subjects will be summarised. For continuous variables, such as weight, the mean, standard deviation, median and range will be presented. For categorical variables, such as gender, the proportion of subjects in each category will be presented.

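### Babies who leave mOm early, after a serious event or over temperature concerns, mostly cannot form a completed set and are in effect replaced, which conflicts with the intention-to-treat statement (minor)

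*Combined protocol and SAP*

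**What the plan says.** Section 2.1.2 gives two routes out of mOm.

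- **Serious event.** If the subject or the incubator "has any unforeseen serious adverse event whilst the baby is in the mOm incubator the subject will immediately be removed from the study", and the baby goes to standard care. This removes the baby from the study as well as from the device.
- **Clinical concern.** Where there is worry about temperature stability or anything else, the attending clinician may transfer the baby to a standard incubator at any time. Study withdrawal is not mentioned here.

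Section 6.4 adds a withdrawal reason that applies in either incubator: "An unanticipated serious adverse event (e.g. SAE or SADE) which requires immediate change to alternative treatment". For a withdrawn baby it asks only that "the reason(s) for withdrawal will be documented where possible".

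On numbers, Section 5 states: "The aim is to collect 36 completed data sets for analysis; to achieve this approximately 40 babies will be recruited", and "recruitment will be stopped once 36 completed data sets are available". Section 8 states: "Thirty-six completed datasets are required for the analysis to be valid". It defines a complete set as at least 19 of 24 hourly temperature readings in each incubator type. Section 8 also commits to intention-to-treat analysis of all data, and judges mOm against the standard incubator from a 95% confidence interval for fluctuation in each.

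The plan does not define the intention-to-treat set, has no missing-data rule, and does not say whether a withdrawn baby's partial readings are used.

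**The concern.** The plan gives two incompatible accounts of who is analysed. Intention-to-treat points to every randomised baby. The completeness rule and the recruitment stopping rule point to completers. Under the second account, a baby can fall out of the temperature analysis because of what happened to it in mOm, and another baby takes its place.

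This matters because the hypothesis in Section 2 is that mOm performs as well as the standard incubator, and the per-incubator intervals are the evidence. If babies who leave mOm early also fluctuated more while in it, leaving them out makes mOm look steadier than it was. The move for temperature concerns is tied most closely to the endpoint, since the reason for leaving is the quantity being measured.

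**Working it through.** **Inputs.** From Section 8: 36 completed sets; 19 of 24 readings per incubator type; interval half-width ±0.33 degrees. From Section 5: about 40 babies recruited; two consecutive 24-hour periods. Assumed: 1:1 order (the ratio is not stated), serious events spread evenly over the 24 mOm hours, and no missed readings before the event.

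**The plan's own figures.**
- Compliance: 19/24 = 79.2% (stated as 79%).
- Allowance for incomplete babies: 40 − 36 = 4, and 4/40 = 10%, for all reasons together.
- Half-width: 1.96 × SD/√36. The SD is not stated; SD = 1.0 gives 0.327, which matches ±0.33.

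**Share of babies removed for a serious event in mOm who cannot complete.**

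Share = P(mOm first) × 1 + P(mOm second) × P(removed before the 19th mOm reading).

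- mOm first: there is no study period in the standard incubator, so 100% fail.
- mOm second: the 19th reading falls at hour 18 (readings at hours 0 to 23) or hour 19 (hours 1 to 24), so 18/24 = 75.0% or 19/24 = 79.2% fail.
- Overall at 1:1: (100 + 75.0)/2 = 87.5%, or (100 + 79.2)/2 = 89.6%.
- If 30% to 70% of removals are in mOm-first babies: 0.3 + 0.7 × 0.75 = 82.5%, up to 0.7 + 0.3 × 19/24 = 93.8%.
- At 1:1 with any timing: (100 + 0)/2 = 50% to (100 + 100)/2 = 100%.

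A baby moved out over temperature concerns may stay in the study, so only the mOm count decides. It cannot complete if it leaves mOm for good before its 19th mOm reading.

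**Possible effect on the mOm mean (illustration only).** Suppose k replaced babies had a mOm fluctuation d degrees above the completers' mean. Leaving them out lowers the mOm mean by d × k/(36 + k):

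| k | d = 0.5 | d = 1 | d = 2 |
|---|---|---|---|
| 1 | 0.014 | 0.027 | 0.054 |
| 4 | 0.050 | 0.100 | 0.200 |

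One baby with a 1-degree excess moves the mean by 0.027/0.33 = 8% of the planned half-width. The k = 4 row gives the whole all-cause allowance to exits from mOm, which is unlikely.

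**A check on the remedy.** Section 8 does not fix the fluctuation measure. If it were a range, it would grow with the number of readings. For independent normal readings the expected range is about 2.53 SD with 6 readings, 3.90 SD with 24 and 4.36 SD with 42. A mOm record cut at 6 readings would show a range 1 − 2.53/3.90 = 35% below that of a full record. Pooling truncated mOm records on a range would therefore favour mOm by construction.

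**The case against.** The strongest reply has four parts.

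- **Removal is a safety choice and events are still reported.** This stands. Serious events are reported under Section 7.4. Device events are a secondary outcome (Section 4.2.4), and Section 7.1 lists hypothermia and hyperthermia as recordable events. An ongoing event falls outside the recording cut-off: "unless a device related adverse event is on-going in which case it will be monitored until resolved". For device-caused events there is also a halt: "if the adverse event is a serious device adverse event, the study will be halted with immediate effect". A serious mOm failure would therefore be visible. None of this says how the baby's temperature readings are analysed.
- **The numbers are small.** Probably so. Babies must be clinically stable at entry, and mOm exposure is 24 hours.
- **Intention-to-treat already keeps these babies.** It can be read that way, but no rule says so or says how, and the text on completed sets points the other way.
- **Adding partial records can itself mislead.** This stands. Besides the range problem, readings taken after a serious event come from a baby who may no longer fit the clinically stable population of Section 3.1, and standard care need not mean a standard incubator. The fix has to respect both limits.

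A reader might infer that withdrawal for serious events is written for mOm alone. Section 6.4 rules that out, because it covers both incubators. Only the automatic removal in Section 2.1.2 is specific to mOm, and that stricter trigger is defensible.

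**Conclusion.** The concern holds as a minor point. Following the stated rules can select the completed sets on events in the mOm period, which conflicts with the intention-to-treat commitment. About 88% to 90% of babies removed for serious events would fail the completeness rule under 1:1 order and even timing, and 50% to 100% with any timing. That replacement occurs is an inference from the recruitment stopping rule; the plan does not use the word.

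Two stronger readings are not supported. A reader might infer that the comparison will be biased in favour of mOm. The documents give no event rate, and serious events are defined by clinical consequence rather than by temperature, so that direction is possible but not established. A reader might also infer that every removed baby is lost. A mOm-second baby with 19 mOm readings already recorded, and enough standard readings, still counts.

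**What to change.** 1. **Sections 2.1.2 and 6.4.** Replace removal from the study with removal from the mOm incubator. Keep both triggers and immediate transfer to standard care. State that a baby with a serious event in either incubator is not placed in, or returned to, mOm for the study. With parental agreement, continue adverse-event recording and routine observations to hour 48, and say so in Section 7.1.
2. **Section 8.** Keep the 36 completed sets. Beside them, add an analysis of all randomised babies that uses every mOm reading up to removal, attributed to the incubator actually used. Use a measure that does not grow with the number of readings, such as the proportion of readings outside 36.5 to 37.5 degrees or the within-baby variance, and not a range. The proportion is the safer choice, because serially correlated readings can make the variance of a short record too small. Show readings taken after the event descriptively only.
3. **Reporting.** Tabulate all early exits by incubator, period and reason, including moves for temperature concerns. Add a worst-case sensitivity analysis that counts exit from mOm for a serious event or temperature concern as failure of temperature control.

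**Cost.** Protocol wording, one extra analysis and a little non-invasive charting. Routine observations are normally three-hourly (Section 5), so even hourly recording adds at most 48 − 48/3 = 32 observation sets per removed baby. The worst-case analysis is deliberately strict on mOm, since a serious event need not be a temperature failure, and should be labelled so.

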7.4 Reporting of Adverse Events

All SAEs / SADEs must be reported by the Investigator to the Sponsor within 24 hours of learning of the incident, by the completion and emailing of an SAE report form, a copy of which will be available in the ISF. Notification of the SAE should be made by phone/email, then the SAE form emailed even if not entirely complete, within the 24-hour period of awareness.

The Sponsor will then liaise with the Chief Investigator and report the SAE to the REC, and the NHS Trust Risk reporting mechanisms (Datix). If deemed possibly device related, it will also be reported to the MHRA and the other PIs and SIs involved in the study.

All adverse events including AEs, ADEs, SAEs and SADEs which occur during the participation in the clinical study must also be recorded in the patient's notes and on the Adverse Event log within 10 working days and will be tracked by the Sponsor representative through regular site monitoring.

Severity of AEs must be identified. Table 2 provides definitions to be used to assess AEs.

TABLE 2: DEFINITIONS OF SEVERITY FOR ADVERSE EVENTS

Mild:	Symptom is only slightly noticeable to the subject or does not cause discomfort; does not negatively influence functioning; prescription drugs not required for relief of symptom but may be prescribed.
Moderate:	Symptom is of a sufficient severity to cause discomfort; performance of daily activities is negatively influenced; treatment for symptom may be needed.
Severe:	Symptom causes severe discomfort and incapacitation having significant impact on the subject's performance of daily activities; treatment for symptom may be given and/or subject's hospitalization may be extended.
Life Threatening:	An event that places the subject at immediate risk of death from the event.
Fatal:	An event that was the direct cause of the subject's death.

“Severe”, “Life-Threatening” or “Fatal” AEs that are determined to be “causally related” to the procedure are to be reported to the Sponsor within 24 hours of the site's knowledge of the event (See definition in Table 3).

TABLE 3: DEFINITIONS OF RELATIONSHIP OF ADVERSE EVENTS

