9. ETHICS

9.1 Declaration of Helsinki

This study will be conducted according to the guidelines established in the Declaration of Helsinki⁷.

Subjects will be free to withdraw from the study at any time without prejudice to their subsequent treatment. In the instance of SADEs occurring the Sponsor and/or CI may decide to stop the study, with immediate effect, on grounds of patient safety at which point all subjects would move into the conventional standard care pathway.

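### The Section 7.4 reporting chain does not support the immediate halt in Section 2.1.2 at other sites, and Section 9.1 words the stop as discretionary

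*Combined protocol and SAP*

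**What the plan says.** Three sections of the combined protocol and SAP bear on what follows a serious device event.

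- **Section 2.1.2 (risks).** For the affected baby, "the subject will immediately be removed from the study and placed into standard care". For the study, "if the adverse event is a serious device adverse event, the study will be halted with immediate effect", and it resumes only when the Sponsor and Chief Investigator are satisfied that the problem is resolved. The section also lets the attending clinician move any baby in a mOm incubator to a standard one at any time, and adds: "A spare standard incubator will always be available for this purpose".
- **Section 9.1 (Declaration of Helsinki).** "In the instance of SADEs occurring the Sponsor and/or CI may decide to stop the study, with immediate effect", on patient-safety grounds, "at which point all subjects would move into the conventional standard care pathway".
- **Section 7.4 (reporting).** "All SAEs / SADEs must be reported by the Investigator to the Sponsor within 24 hours of learning of the incident". Notification "should be made by phone/email, then the SAE form emailed even if not entirely complete, within the 24-hour period of awareness". The Sponsor then liaises with the Chief Investigator and reports onward. "If deemed possibly device related, it will also be reported to the MHRA and the other PIs and SIs involved in the study".

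Section 5 describes a multi-centre cross-over with 24 hours in each incubator type. About 40 babies are to be recruited to give 36 complete datasets, with a nine-month recruitment target.

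**The concern.** The same kind of event has two rules. In 2.1.2 the halt is automatic; in 9.1 a stop is something the Sponsor and/or Chief Investigator may choose. The only sentence that expressly sends all babies to standard care belongs to the second rule. Section 2.1.2 names an action for the affected baby but none for others who are in a mOm incubator at that moment.

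The second and larger difficulty is how the halt reaches other sites. The reporting site's team already knows of the event, but staff elsewhere can act only once told. The one route that the protocol describes has a 24-hour first step and an untimed, conditional second step.

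What is at stake is the purpose of the halt: keeping other babies away from a fault that their incubator may share. The SADE definition in Section 7.3 includes events that could have been serious without intervention, so near-misses also trigger it. The endpoint and its analysis are not affected.

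**Working it through.** **1. Wording, side by side**

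| | Section 2.1.2 | Section 9.1 |
|---|---|---|
| Trigger | Serious device adverse event | SADEs |
| Study-level action | Halt, mandatory | Stop, discretionary |
| Timing | Immediate | Immediate once decided |
| Affected baby | Moved at once | Covered by the move of all |
| Other babies in mOm | Not stated | All move, once a stop is decided |

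The protocol does not say whether *halt* and *stop* are the same act.

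**2. Timing to another site under 7.4**

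- Site to Sponsor: up to 24 h from awareness. Phone/email comes before the form, but both share that limit.
- Sponsor to other investigators: after liaison with the Chief Investigator, and if the event is deemed possibly device related. No time limit is given, and the text does not say who makes the judgement.
- Longest delay within the stated limit: 24 h plus an unspecified interval.
- Length of a mOm period (Section 5): 24 h.

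A baby elsewhere who enters mOm when the event becomes known could therefore finish the whole period before any notice that 7.4 requires.

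**3. Size**

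The protocol gives no figure for this exposure, so there is none to reproduce.

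Inputs from Section 5: 40 babies, one mOm day each, nine months = 9 × 30.4375 = 273.9 days. Assumptions: *S* equal sites, with *S* from 2 to 4 (the number is not given), and even recruitment.

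- Babies at other sites in mOm at any moment: r = 40 × (S − 1)/S ÷ 273.9.
- Other-site mOm baby-hours during a 24 h delay: 24 × r.
- Chance that at least one other-site baby is in mOm during those 24 h (Poisson): 1 − exp(−2r). The factor 2 counts babies already in mOm plus those who start within the 24 h.

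| S | r | 24 × r | 1 − exp(−2r) |
|---|---|---|---|
| 2 | 20/273.9 = 0.073 | 1.75 h | 0.136 |
| 3 | 26.67/273.9 = 0.097 | 2.34 h | 0.177 |
| 4 | 30/273.9 = 0.110 | 2.63 h | 0.197 |

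Each further 24 h in the untimed second step adds the same baby-hours again. If recruitment took half as long (4.5 months, purely illustrative), the baby-hours double to 3.5 to 5.3 and the chances become 25% to 36%.

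**4. Datasets lost if all babies in mOm are moved**

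- Other babies in mOm at any moment, all sites: 39/273.9 = 0.142.
- Section 8 accepts a period with 19 of 24 hourly readings, so about 19/24 of these would be incomplete: 0.142 × 19/24 = 0.11.
- Babies in a first, standard period who cannot cross over during the halt (half of the 40): 20/273.9 = 0.07.
- Total: 0.11 + 0.07 = 0.18, so about 0.1 to 0.2 babies per SADE, depending on whether the second group is counted.

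**5. Incubator capacity**

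The chance that a second baby is in mOm at the affected site is 1 − exp(−(40/S − 1)/273.9): 0.067, 0.044 and 0.032 for S = 2, 3 and 4.

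**The case against.** The strongest reply is that the sections can be read together. Section 2.1.2 describes a pause with a restart condition, and 9.1 can be read as a further, discretionary termination. If the two terms instead mean the same thing, 9.1 supplies the move of all subjects. On either reading, a study halted with immediate effect does not naturally leave babies in its investigational device. Clinicians may also move any baby at any time. This largely stands. A reader might infer that the protocol would keep other babies in mOm during a halt, or that 9.1 cancels the mandatory halt; the documents support neither. What remains is that the text leaves staff to work this out.

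A second reply is that the 24 hours in 7.4 is an outer limit for reporting all serious events, while the immediate halt in 2.1.2 is a separate duty. A Sponsor that let mOm use run on elsewhere for 24 hours would meet 7.4 but not 2.1.2. That is also right: the documents do not show that such a delay is intended or endorsed. But 2.1.2 gives no route by which the halt reaches another site, and 7.4 is the only route described. Freedom to move a baby does not help staff who have not been told.

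Third, 2.1.2 binds the study to Sponsor SOPs and study manuals, which are not public and may contain a faster chain. That cannot be excluded. The protocol does not point to one, and an SOP would not reconcile 2.1.2 with 9.1.

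**Conclusion.** The point holds as a worthwhile, low-cost improvement. The mismatch between the automatic halt and the discretionary stop is real but minor. The more substantive gap is that reporting within the limit stated in 7.4 does not ensure an immediate halt at other sites, because the permitted notice time is at least as long as a mOm period.

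The expected exposure is small: 1.8 to 2.6 other-site baby-hours per SADE for a 24-hour delay, and a 14% to 20% chance that any other-site baby is in mOm during it. These figures rest on 2 to 4 equal sites and 40 babies recruited evenly over nine months. They are conditional on a SADE, whose rate the documents do not give. They measure time in the device, not harm. Confidence is moderate, because the SOPs and manuals cannot be seen.

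**What to change.** Three wording changes in one amendment:

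1. **Section 9.1:** any SADE triggers the automatic halt in Section 2.1.2; the Sponsor and/or Chief Investigator may in addition terminate the study, in which case all subjects move to standard care.
2. **Section 2.1.2:** during a halt no baby is placed in a mOm incubator at any site, and every baby then in one moves to a standard incubator as soon as clinically safe.
3. **Section 7.4:** a suspected SADE is phoned to the Sponsor on awareness. The Sponsor tells all principal investigators within a short limit that it fixes in the protocol, for example the same day, without waiting for the relatedness judgement. The written form stays due within 24 hours.

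The third change should carry an actual limit; repeating the word *immediately* would leave the gap open.

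The cost is about 0.1 to 0.2 incomplete datasets per SADE, replaced under the existing rule of recruiting until 36 are complete. Some stable babies will be moved after events that prove unrelated to the device, which is why the move is tied to clinical safety. Each site also needs enough standard incubators. Section 2.1.2 promises one spare, and the chance of a second baby in mOm at the affected site is about 3% to 7% under the nine-month assumptions.
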